**6.4.**

[REDACTED]

- | [Redacted]
- | [Redacted]
- | [Redacted]
- | [Redacted]
- | [Redacted]
- | [Redacted]
- | [Redacted]
- | [Redacted]

## 7. MULTIPLE COMPARISONS AND MULTIPLICITY

A fixed-sequence (hierarchical) testing procedure will be implemented to control the type 1 error rate at 0.05.

Testing of statistical significance at a 2-sided alpha of 0.05, fremanezumab 675-mg sc treatment group versus placebo group, will be performed for the primary endpoint. If the primary endpoint meets statistical significance, then each of the key secondary endpoints will be tested for significance in a pre-specified order at a 2-sided alpha of 0.05. If and when any  $p > 0.05$ , no further comparisons will be interpreted inferentially.

The sequence of comparisons will be as follows:

1. **Primary endpoint** (mean change from baseline (baseline period) in the monthly average number of headache days of at least moderate severity during the 12-week period after the first dose of the IMP)
2. **1st key secondary endpoint** (proportion of patients reaching at least 50% reduction from baseline (baseline period) in the monthly average number of headache days of any severity during the 12-week period of treatment with the IMP)
3. **2nd key secondary endpoint** (mean change from baseline (visit 2) in disability score, as measured by the 6-item Headache Impact Test (HIT-6) at week 12 after the first dose of the IMP)

## 8. SAFETY ANALYSIS

### 8.1. General

For double-blind treatment period (up to visit 5), the safety analysis set will be used for all safety analyses. Summaries will be presented using descriptive statistics by treatment group as actually received unless otherwise stated and overall.

For open-label treatment period (visits 5 to 8/EOT/EOS/ET), OL-ITT analysis set will be used for safety analyses. Changes from baseline or change from visit 5 will be presented. Summaries will be presented using descriptive statistics overall. **The data will be analyzed after the completion of the study.**

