	• mean change from baseline (visit 2) in the assessment of patient satisfaction, as measured by the Patient Global Impression of Change scale, at 4, 8, and 12 weeks after the first dose of the IMP

[figure not shown]
Objectives	Endpoints
A secondary objective of the study is to evaluate the safety and tolerability of fremanezumab administered sc in adult patients with PTH compared with placebo and during the open-label period.	The safety and tolerability endpoints are:
	
 
occurrence of adverse events during the study
 

	
 
clinically significant changes in physical examinations, including body weight
 

	
 
clinical laboratory (serum chemistry, hematology and coagulation, and urinalysis) test results at each visit
 

	
 
vital signs (blood pressure, respiratory rate, body temperature, and pulse) measurements at each visit Note: Oxygen saturation and respiratory rate will be measured in cases of suspected anaphylaxis and severe hypersensitivity.
 

	12-lead electrocardiogram (ECG) findings at each visit
	use of concomitant medication during the study
	
 
number (%) of patients who did not complete the study (day 168,end-of-study [EOS])
 

	
 
number (%) of patients who did not complete the study due to adverse events
 

	• local tolerability at the injection site (ie, erythema, induration, ecchymosis, and pain) at the following time points postdose: day 0, day 28, and day 56
	
 
hypersensitivity reaction assessment
 

	Columbia Suicide Severity Rating Scale (C-SSRS)
The immunogenicity objective is to evaluate the immunogenicity of fremanezumab and the impact of antidrug antibodies (ADAs) on clinical outcomes in patients exposed to fremanezumab.	The immunogenicity endpoints are ADA incidence and characteristics (eg, titer, kinetics, and neutralizing activities).

ADA=antidrug antibody; C-SSRS=Columbia Suicide Severity Rating Scale; ECG=electrocardiogram; HIT-6=6-item Headache Impact Test; IMP=investigational medicinal product; PTH= posttraumatic headache; sc=subcutaneous.

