## 9.7. Safety Analysis

Safety analyses will be performed on the safety analysis set (Section 9.2.3).

Safety assessments and time points are provided in Table 1.

All adverse events will be coded using the Medical Dictionary for Regulatory Activities. Each patient will be counted only once in each preferred term or system organ class category for the analyses of safety. Summaries will be presented for all adverse events (overall and by severity), adverse events determined by the investigator to be related to test IMP (ie, reasonable possibility; see Section 7.1.4) (defined as related or with missing relationship) (overall and by severity), serious adverse events, and adverse events causing withdrawal from the study. Summaries will be presented by treatment group and for all patients. Patient listings of serious adverse events and adverse events leading to withdrawal will be presented.

Changes in laboratory, ECG, and vital signs measurements data will be summarized descriptively. All values will be compared with predefined criteria to identify potentially clinically significant values or changes, and such values will be listed.

The use of concomitant medications will be summarized by therapeutic class using descriptive statistics. Concomitant medications will include all medications taken while the patient is treated with test IMP.

Safety data will be summarized descriptively overall and by treatment group. For continuous variables, descriptive statistics (n, mean, SD, median, minimum, and maximum) will be provided for actual values and changes from baseline to each time point. For categorical variables, patient

counts and percentages will be provided. Descriptive summaries of serious adverse events, patient withdrawals due to adverse events, and potentially clinically significant abnormal values (clinical laboratory or vital signs) based on predefined criteria will be provided as well.

If any patient dies during the study, a listing of deaths will be provided and all relevant information will be discussed in the patient narrative included in the CSR.

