### **4.2. Specification of Baseline Values**

For analyses of the double-blinded treatment period, baseline is the last observed data before the administration of the first dose of the IMP, unless otherwise noted. For data collected in the e-diary daily, baseline will be derived from the baseline period (from the day of the informed consent to before the administration of the first dose of the IMP) and prorated to 28 days if the number of days in the baseline period is not equal to 28. Details are provided in Section 6.1.

For analyses of the open label treatment period, the baseline is the observed data at visit 5, unless otherwise noted.

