### **8.4. Injection Site Assessments**

Injection site assessments will be performed immediately (+10 minute) and 1 hour ( $\pm 15$  minutes) after receiving each dose of the IMP at visits 2, 3, and 4. The injection sites will be assessed for erythema, induration, and ecchymosis. More details are in Section 7.9 of the study protocol.

Injection-site reactions should be recorded as adverse events. Injection-site related adverse events will be summary as indicated in Section 8.3.

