### **8.5. Hypersensitivity/Anaphylaxis**

Patients will be assessed for suspected anaphylaxis/hypersensitivity reactions during and after administration of the IMP at visits 2, 3, and 4. Data will be summarized using descriptive statistics.

The number of patients with suspected anaphylaxis/hypersensitivity reactions and number of suspected anaphylaxis/hypersensitivity reactions per patient will be summarized using descriptive statistics.

The relative time of suspected event will be calculated as date/time of suspected event - date/time of most current IMP administration and summarized using descriptive statistics. If a patient has more than one suspected anaphylaxis reactions, the earliest time will be used for the calculation.

Data will be listed.

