## **10. PHARMACOKINETIC ANALYSIS**

Pharmacokinetic plasma concentration results for fremanezumab will be tabulated descriptively at each planned sampling time point. The summary will be based on the safety analysis set. At the open-label period, pharmacokinetic plasma concentration results will be tabulated descriptively at each planned sampling time point per treatment group. The plasma concentration will be listed by scheduled visits, time points and treatment.

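### Open-label safety tables put first-time and continuing fremanezumab patients in one column, which is narrower than the protocol and is not declared as a change

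*SAP*

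**What the plan says.** SAP Section 8.1 treats the two periods differently. Double-blind safety is shown by treatment actually received and overall. For the open-label period, analysed on the OL-ITT set, the text is "Changes from baseline or change from visit 5 will be presented. Summaries will be presented using descriptive statistics overall". SAP Section 3.2 defines OL-ITT as randomized patients given at least one open-label dose and sets no grouping within it.

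Other places bear on this:

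- Protocol Section 9.7: "Safety data will be summarized descriptively overall and by treatment group". The sentence is not limited to the double-blind period.
- SAP Section 10: "At the open-label period, pharmacokinetic plasma concentration results will be tabulated descriptively at each planned sampling time point per treatment group".
- SAP Section 4.2: "For analyses of the open label treatment period, the baseline is the observed data at visit 5, unless otherwise noted".
- SAP Section 8.5: "Patients will be assessed for suspected anaphylaxis/hypersensitivity reactions during and after administration of the IMP at visits 2, 3, and 4". Protocol Table 1 schedules the same assessment at visits 2 through 7.
- Protocol Section 2.1 makes it a secondary objective to evaluate safety and tolerability "in adult patients with PTH compared with placebo and during the open-label period".
- The SAP Introduction gives the SAP precedence where the two documents differ, and SAP Section 17 lists no changes from the protocol.

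**The concern.** The open-label set mixes two exposures. A former placebo patient meets the drug for the first time at visit 5. A patient from the active arm has already had three doses and has stayed in the study. One overall column describes neither group. If reactions or laboratory shifts cluster in early exposure, continuing patients dilute them; if problems build with longer exposure, first-time patients dilute those.

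The reference value makes this worse. SAP Section 8.1 offers change from baseline or change from visit 5 without saying which applies to which summary. Visit 5 is a drug-free value for one group and an on-drug value for the other.

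At stake is the safety information from the former placebo patients, who with 1:1 allocation supply up to about half of all first exposures to fremanezumab in a trial of 87 patients.

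**Working it through.** The documents state no figure for open-label safety, so there is nothing to reproduce. The check is a comparison of texts followed by a sizing.

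**Texts.** SAP Section 8.1 asks for the group split in the double-blind period and omits it for the open-label period ("Summaries will be presented using descriptive statistics overall"). Protocol Section 9.7 has the split without limit of period. SAP Section 10 shows that the sponsor regards treatment group as meaningful after visit 5. SAP Section 17 does not record the narrowing.

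**Do the groups differ at visit 5?** Inputs: mean half-life 32.2 to 36.2 days (Protocol Section 1.2.2.1) and doses 28 days apart. Assumptions: one compartment, first-order elimination, absorption ignored. The fraction left after one interval is r = 2^(−28/half-life).

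| | 32.2 days | 36.2 days |
|---|---|---|
| r | 0.547 | 0.585 |
| Doses' worth on board at visit 5, r + r² + r³ | 1.01 | 1.13 |
| Fraction of steady-state trough, 1 − r³ | 0.84 | 0.80 |

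A patient from the active arm reaches visit 5 with about one dose on board, at 80–84% of steady-state trough. A former placebo patient has none.

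**Column sizes.** 87 patients at 1:1 give 43 and 44. Applying the planning discontinuation rate of 10% (Protocol Section 16.1, new wording for Section 9.1), 87 × 0.9 ≈ 78, or 39 and 39.

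**Adverse event rates.** Pooled rate = (x₁ + x₂)/(n₁ + n₂). The rates below are assumed for illustration, with 39 patients per group and exact (Clopper-Pearson) 95% intervals.

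| Assumed rates, first / continuing | First exposure | Continuing | Overall column |
|---|---|---|---|
| 10% / 10% | 4/39 = 10.3% | 4/39 = 10.3% | 8/78 = 10.3% |
| 20% / 10% | 8/39 = 20.5% (9.3–36.5) | 4/39 = 10.3% (2.9–24.2) | 12/78 = 15.4% (8.2–25.3) |
| 30% / 10% | 12/39 = 30.8% (17.0–47.6) | 4/39 = 10.3% (2.9–24.2) | 16/78 = 20.5% (12.2–31.2) |

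With no loss (43 and 44 patients), the middle case gives 9/43 = 20.9%, 4/44 = 9.1%, and 13/87 = 14.9% overall. Where the two rates are equal, pooling hides nothing.

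**Changes in a continuous measure.** Suppose the drug shifts a measure by D and the groups are equal in size.

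- From visit 5: former placebo patients shift by D. Continuing patients, already near steady state, shift by about 0. Pooled: (D + 0)/2 = D/2. If continuing patients still move a little in the same direction, the pooled figure lies somewhat above half.
- From the value before dose 1: both groups go from drug-free to on-drug. Pooled: (D + D)/2 = D.

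The halving therefore belongs to only one of the two references that SAP Section 8.1 allows.

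**The case against.** The best defence is that treatment group has no clear meaning once everyone is on the same drug. Protocol Section 9.7 does not mention the open-label period, and Protocol Section 9.2.3 groups safety patients by what they actually received. This has some force: the mismatch is an unresolved ambiguity more than a flat contradiction. But the open-label pharmacokinetic wording points the other way, and Section 17 leaves the matter unaddressed.

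Second, the double-blind tables already show doses 1 to 3 against randomized placebo, which is better evidence on first exposure than an uncontrolled column. That stands and limits the harm. It does not justify leaving the second half of the first exposures unseparated.

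Third, SAP Section 8.3 lists adverse event preferred terms by patient and treatment group, and open-label data are analysed after unblinding, so the split can be recovered. True, but a listing is not a summary table.

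Four stronger readings are tempting, and the documents do not support them:

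- A reader might infer that the open-label objective cannot be answered. The objective asks for no comparison by former arm, and a pooled description meets it.
- A reader might infer that visit 5 is the only baseline. SAP Section 8.1 also allows change from baseline, and SAP Section 4.2 permits exceptions.
- A reader might infer that open-label HIT-6, SF-12 and PGIC are pooled too. SAP Section 6.1 presents efficacy by randomized group unless otherwise noted, and the detail of Section 6.4 is redacted.
- A reader might infer that SAP Section 8.4 is wrong to describe injection-site assessment "after receiving each dose of the IMP at visits 2, 3, and 4". The endpoint in SAP Section 1.3 is itself limited to days 0, 28 and 56, which are those visits. The hypersensitivity endpoint carries no such limit.

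**Conclusion.** The point holds as a reporting gap. The open-label safety tables cannot tell first exposure from continued exposure, the plan is narrower here than Protocol Section 9.7, and the narrowing is undeclared. The choice between two reference values is left open.

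The size depends on how far the two groups differ, which the documents do not tell us. If their rates are equal, nothing is lost. If they are near 20% and 10%, the table shows about 15%. An effect seen only on first exposure is halved in a change from visit 5, assuming equal groups and little further change in continuing patients. It is not halved in a change from the pre-dose-1 value. The pharmacokinetic figures rest on a one-compartment simplification and serve only to show that the groups differ at visit 5.

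Importance is minor to moderate. The output is descriptive, the data exist, and the primary efficacy analysis is untouched. It is worth correcting because the correction is cheap.

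**What to change.** 1. In SAP Section 8.1, present open-label safety by double-blind arm (placebo to fremanezumab; fremanezumab to fremanezumab) and overall.
2. Replace the open choice of reference with a stated one for each summary. Within any overall column use the same reference for all patients; for example, show both change from the pre-dose-1 value and change from visit 5, each by arm. Do not give the two arms different baselines and then pool them, because that column would average changes from different starting points.
3. In SAP Section 8.5, extend the hypersensitivity summary to visits 5 to 7, where Protocol Table 1 already collects the data.
4. If the overall-only presentation is kept, list it in SAP Section 17 as a change from Protocol Section 9.7.

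The cost is SAP wording and two further table columns, with no new data. Each column would hold about 39 to 44 patients, so intervals are wide and the comparison between columns stays descriptive.

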### 8.2. Duration of Exposure to Study Drug

#### 8.2.1. Double-Blind Treatment Period

During the double-blind treatment period patients will receive 3 sc injections of fremanezumab or placebo at visit 2, visit 3, and visit 4.

Duration of the double-blind treatment period (days) for a patient is defined as the number of days a patient is in the double-blind treatment period and calculated as the date of visit 5 - the first date of the IMP + 1. For patients who do not complete double-blind treatment period, date of visit 5 will be estimated as the date of last IMP administration in double-blind treatment period + 27. Dosing visit interval (days) is defined as the number of days between dosing visit (dose 1 and dose 2; dose 2 and dose 3) and calculated as date of next dosing - date of current dosing.

Duration of the double-blind treatment period (days), dosing visit interval (days), the number of doses received, and total number of injections received will be summarized using descriptive statistics. Summary will be presented by treatment group.

IMP administration and accountability data will be listed.

#### 8.2.2. Open-Label Treatment Period

During the open-label treatment period patients will receive 3 sc injections of fremanezumab at visit 5, visit 6, and visit 7.

Duration of the treatment (days) in the study (both in double-blind and open label) for a patient is defined as the number of days a patient is in the study and calculated as the date of visit 8 - the first date of the IMP + 1. Duration of the treatment (days) in the open-label treatment period for a patient is defined as the number of days a patient is in the open-label treatment period and calculated as the date of visit 8 - the date of the IMP at visit 5 + 1. For patients who are do not complete open-label treatment, date of visit 8 will be estimated as the date of last IMP administration + 27.

Duration of the treatment (days) in the study and in the open-label period will be summarized using descriptive statistics.

IMP administration and accountability data will be listed.

### **8.3. Adverse Events**

Adverse events will be recorded from time informed consent is obtained through the end of study participation.

The following are considered protocol-defined adverse events of special interest (PDAESI) to be sent to the sponsor's Global Patient Safety and Pharmacovigilance Department for evaluation: ophthalmic-related adverse events of at least moderate severity, events of possible drug-induced liver injury (AST or ALT  $\geq 3 \times$  ULN, total bilirubin  $\geq 2 \times$  ULN, or international normalized ratio  $> 1.5$ ), Hy's Law events, or events of anaphylaxis and severe hypersensitivity.

All adverse events will be coded using MedDRA. Each patient will be counted only once in each preferred term or SOC category for the analyses of safety. Summaries will be presented for all adverse events (overall and by severity), adverse events determined by the investigator to be related to test IMP (defined as related or with missing relationship) (overall, overall by severity, serious AEs, PDAESI), serious adverse events, PDAESI, and adverse events causing withdrawal from the study. Adverse events with the missing flag indicating serious will be excluded from the summary of serious adverse events but included in the summary of non-serious adverse events.

Summaries for injection site adverse events will be presented (overall and by severity).

Listings for deaths, serious adverse events, adverse events leading to treatment withdrawn, adverse events leading to study discontinuation, adverse event requiring concomitant or additional treatment, injection site adverse events, PDAESI, and hypersensitivity and suspected anaphylaxis/hypersensitivity reactions related adverse events will be presented. In addition, listings for MedDRA dictionary terms for adverse event descriptions and adverse event preferred terms by patient number and treatment group will be presented.

Spontaneous abortion or an elective abortion due to developmental anomalies will be reported as a serious adverse event (protocol Section 7.2). These serious adverse events will be listed separately if applicable.

Summaries will include treatment-emergent adverse events which are defined as adverse events occurring at or after the first dose of the IMP. The listing will include all adverse events recorded.

Adverse events for patients who did not meet screening criteria will be listed.

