The onset and end dates, duration (in case of adverse event duration of less than 24 hours), action taken regarding IMP, treatment administered, and outcome for each adverse event must be recorded both on the source documentation and the CRF.

The severity, seriousness, and relationship of each adverse event to the test IMP and study procedures, as judged by the investigator, must be recorded as described below.

Further details are given in the Safety Monitoring Plan.

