#### **Data Quality Control**

Data Management is responsible for the accuracy, quality, completeness, and internal consistency of the data from this study. Oversight will be carried out as described in the sponsor's SOPs for clinical studies. Day-to-day data management tasks for this study are

delegated to a contract organization, and these functions may be carried out as described in the SOPs for clinical studies at that organization. These SOPs will be reviewed by the sponsor before the start of data management activities.

Data will be verified by the study monitor using the data source and reviewed by Data Management using both automated logical checks and manual review. Data identified as erroneous or data that are missing will be referred to the investigational center for resolution through data queries. Any necessary changes will be made in the clinical database, and data review and validation procedures will be repeated as needed. Data from external sources will be compared with the information available in the CDMS, and any discrepancies will be queried.

Applicable terms will be coded according to the coding conventions for this study.

A final database lock will occur following the end-of-treatment visit (visit 8) of the last patient. At the conclusion of the study, the CDMS and all other study data will be locked to further additions or corrections. Locking the study data represents the acknowledgement that all data have been captured and confirmed as accurate. All data collected will be approved by the investigator at the investigational center. This approval acknowledges the investigator's review and acceptance of the data as being complete and accurate.

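### SAP 8.3 counts adverse events with a missing seriousness flag as non-serious, which can lower the reported serious-event incidence or leave it unchanged but never raise it, and is the reverse of its rule for a missing relationship

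*SAP*

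**What the plan says.** SAP Section 8.3 gives one rule for each of two missing adverse event fields.

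- **Seriousness missing.** "Adverse events with the missing flag indicating serious will be excluded from the summary of serious adverse events"; the sentence continues "but included in the summary of non-serious adverse events".
- **Relationship missing.** The related-event summaries cover "adverse events determined by the investigator to be related to test IMP (defined as related or with missing relationship", so a blank counts as related.

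Protocol Section 9.7 has the same relationship rule ("defined as related or with missing relationship) (overall and by severity), serious adverse events, and adverse events causing withdrawal from the study") but says nothing about missing seriousness. The seriousness rule therefore enters with the SAP. The SAP gives no reason for its direction and plans no alternative count.

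Two protocol provisions bear on how often the rule would operate. Section 7.1.2 requires that "The severity, seriousness, and relationship of each adverse event to the test IMP and study procedures, as judged by the investigator, must be recorded". Appendix P, under Data Quality Control, says that "Data identified as erroneous or data that are missing will be referred to the investigational center for resolution through data queries".

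**The concern.** A blank flag means that seriousness is unknown. Protocol Section 7.1.5.1 reserves the non-serious label for events that meet none of its criteria, which is a determination. The SAP assigns that label when no determination has been recorded. For relationship, the same paragraph resolves the unknown the cautious way.

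The rule also has no exceptions. Section 7.1.5.1 makes a fatal event serious by definition and requires Hy's law cases to be reported as serious, and SAP Section 8.8.1 puts Hy's law cases into serious adverse event reporting. Read literally, a blank flag on such an event would still remove it from the serious-event summary, in tension with both sections. An event with both fields blank would count as related but presumably drop out of the related serious-event summary.

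What is at stake is the count in the serious-event tables. In arms of about 43 patients, one patient is visible in that count.

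**Working it through.** The documents state no serious-event rate and no number of missing flags, so there is no planned figure to reproduce. The check compares the two counting rules.

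**Inputs**
- Counting unit: the patient (SAP 8.3: "Each patient will be counted only once in each preferred term or SOC category for the analyses of safety").
- Enrolment: recruitment stopped at 87 (protocol 3.2), with 1:1 allocation (protocol 3.1).
- Arm size: 87 / 2 = 43.5, so N = 43 or 44. This is an assumption, because the documents do not give the split.
- s = patients in the arm with at least one event flagged serious.
- m = patients in the arm with no event flagged serious but at least one event with a missing flag. The documents give no value, so a range is shown.

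**Formulas**
- SAP rule: s / N.
- Missing counted as serious: (s + m) / N.
- Difference: m / N. Since m cannot be negative, the SAP figure is never the larger of the two.

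**Difference in percentage points**

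| m | N = 43 | N = 44 |
|---|---|---|
| 0 | 0 | 0 |
| 1 | 2.33 | 2.27 |
| 2 | 4.65 | 4.55 |
| 3 | 6.98 | 6.82 |

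Example with N = 43, s = 1, m = 1: the SAP rule gives 1/43 = 2.33%, and the alternative gives 2/43 = 4.65%.

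**Against the true classification.** Suppose k of the m patients really had a serious event, with k between 0 and m. The true incidence is (s + k) / N. The SAP rule understates it by k / N, and the alternative overstates it by (m − k) / N. The two counts bracket the truth, which is the argument for showing both.

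**When nothing moves.** The overall incidence is the same under both rules if no flag is missing, or if the only patients with a missing flag already have another event flagged serious. If the event was truly non-serious (k = 0), the SAP classification is correct.

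**The case against.** The strongest reply is that the rule should almost never operate. Seriousness must be recorded for every event, and missing data are queried with the center. Appendix P treats lock as confirmation that the data are complete and accurate. Serious events also leave a second record: protocol Section 7.1.5.3.1 requires a separate form within 24 hours, even when information is incomplete. A blank flag with no such form is therefore some evidence that the event was not serious. Causality has no comparable second record for a non-serious event, so opposite defaults could be defended and are not in themselves an inconsistency.

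Little would be hidden either way. The event stays in the all-event summaries, and SAP 8.3 lists every recorded event and lists deaths separately. Safety is summarized descriptively (SAP 8.1), so no test depends on the count. The 2.3 points is simply one patient divided by an assumed arm size. Counting every blank as serious could also put a mild injection-site reaction in the serious table with no matching report.

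Most of this stands, and it makes the point a low priority. It does not justify the direction of the rule: the SAP does not give this reasoning, and it does not make the default depend on checking the serious adverse event forms. The over-counting objection is fair, and it is why resolution should come first and both counts should be shown.

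A reader might infer more than the documents support:
- **That serious events will be under-reported.** Nothing shows that any flag will be missing at lock.
- **That the absence of a data monitoring committee makes this worse.** The rule governs summary tables. Protocol Section 3.4 has serious events reviewed as centers report them, and the table rule does not affect that review.
- **That the rule favors fremanezumab.** The same rule applies to both arms, and SAP Section 2.5.2 has the plan finalized before the lock that precedes unblinding.

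**Conclusion.** The point holds as a low-priority improvement to a stated rule. SAP 8.3 resolves an unknown seriousness flag as non-serious, so relative to the cautious count the reported incidence can fall or stay the same but cannot rise. The neighboring rule for relationship goes the other way.

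The size is zero if all flags are resolved before lock, which is the likely outcome. Otherwise it is about 2.3 percentage points per affected patient in an arm. That rests on 43 to 44 patients per arm; the number of affected patients is unknown. Open-label safety summaries are pooled (SAP 8.1), so with at most 87 patients one patient there is at least 1/87 = 1.1 points.

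**What to change.** Replace the sentence in SAP 8.3, before the double-blind lock, with text to this effect:

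1. Every missing seriousness flag is to be resolved before the double-blind lock, by query and by checking against the serious adverse event forms and the criteria in protocol Section 7.1.5.1.
2. Any event whose flag is still missing at lock is counted as serious in the summary and identified in the listing.
3. The serious-event count without such events is shown alongside.

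The cost is a few lines of text and a reconciliation that largely overlaps with existing data management. The downside is that the serious-event count could be slightly too high if a truly non-serious event keeps a blank flag; the second count lets the reader see by how much. If no flag is missing, nothing in the tables changes.
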